8.2. Background and Demographic Characteristics

Subjects' age, height, weight, and baseline characteristics will be summarized using descriptive statistics, while gender, race and other categorical variables will be provided using frequency tabulations. Medical history data including cancer history will be listed.

8.3. Subject Disposition

Subject disposition (analysis population allocation, entered, discontinued, along with primary reason for discontinuation) will be summarized using frequency and percent for both treatment and follow-up phases. A summary of subjects enrolled by site will be provided. Protocol deviations will be summarized using frequency tabulations.

9. OUTCOME MEASURES

9.1. Efficacy Analysis

Tumor response including PD, progression-free survival (PFS), and overall survival (OS) will be assessed by the investigators using RANO 2010 criteria. The overall confirmed response rate will be examined.

Efficacy analysis:

Primary Endpoint

- *The primary endpoint of the study will be 6-month progression-free survival*

Secondary Outcome Measures

- *Safety*
- *Overall survival time*
- *Correlations with established molecular markers (ATRX, TERT promoter and/or IDH1 mutation and MGMT promoter methylation)*
- *Quality of Life*

9.2. Safety Analysis

All subjects will be evaluated for safety analysis if they receive NOVOTTF-200A. The safety data will be presented in individual listings and summary tables, including frequency tables for adverse events and listings of abnormalities for laboratory variables.

Safety analysis:

- *Safety and tolerability of NOVOTTF-200A treatment will be based on the incidence and severity of adverse events and toxicities. Toxicities will be assessed according to the “Common toxicity criteria (CTC), version 4.03”.*

10. ADVERSE EVENTS

10.1. Monitoring, Recording and Reporting of Adverse Events

Data and Safety Monitoring Plan

This is a risk level 1 study, as defined in the Chao Family Comprehensive Cancer Center (CFCCC) Data and Safety Monitoring Plan (DSMP) because this is a high risk UCI investigator-initiated interventional trial where the PI holds the IDE.

The Principal Investigator (PI), co-investigator, clinical research coordinator, and statistician are responsible for monitoring of data and safety for this study, including implementation of the stopping rules for safety and efficacy.

The CFCCC Data and Safety Monitoring Board (DSMB) is an independent body responsible for the safety of study subjects as well as the data integrity of the protocol. Data and safety will be reported to the DSMB with submission of progress reports that include aggregated reports of adverse events, serious adverse events, deviations/violations, and unanticipated problems. In addition, certain adverse events and deviations/violations, and unanticipated problems will be reported promptly to the DSMB for review according to the tables below.

Risk Levels

Risk Level	Definition	Monitoring
Level 1	High Risk - UCI investigator-initiated interventional trials where the PI holds Investigational New Drug (IND) or Investigation Device Exemption (IDE). Example: Gene therapy, dendritic cell products from GMP suite, phase I/II development and phase I studies, first in human, etc.	Two months after subject enrollment
Level 2	Medium Risk - UCI investigator-initiated interventional trials for which IND/IDE is exempt by FDA. Example: Use of commercially available agents for an unapproved indication.	Six months after subject enrollment
Level 3	Low Risk – UCI investigator-initiated interventional trials that is minimal risk. Example: Phase III clinical studies, dietary intervention trials, and after-market studies.	Twelve months after subject enrollment
Exempt	Studies that are industry-sponsored, NCTN-sponsored, and/or trials that are monitored by an external DSMB.	

Recording of Events

All investigator initiated treatment trials require that adverse events, serious adverse events, deviations, and unanticipated problems be entered into the clinical trial management system (CTMS), OnCore. All entries must be entered in OnCore within five (5) days of being aware of

the adverse event, serious adverse event, violation, deviation, or unanticipated problem. Serious violations, deviations/violations, and unanticipated problems that require prompt reporting to the DSMB must be entered into OnCore within 24 hours of knowing of the event. Definitions of events are provided below.

Definitions

Adverse event (AE) - An adverse event is any untoward medical experience or change of an existing condition that occurs during or after treatment, whether or not it is considered to be related to the protocol intervention.

Unexpected Adverse Event [21 CFR 312.32 (a)] – An adverse event is unexpected if it is not listed in the investigator’s brochure and/or package insert; is not listed at the specificity or severity that has been observed; is not consistent with the risk information described in the protocol and/or consent; is not an expected natural progression of any underlying disease, disorder, condition, or predisposed risk factor of the research participant experiencing the adverse event.

Expected Adverse Event - Any event that does not meet the criteria for an unexpected event OR is an expected natural progression of any underlying disease, disorder, condition, or predisposed risk factor of the research participant experiencing the adverse event.

Serious Adverse Event (SAE) [21 CFR 312.32] - defined as *any expected or unexpected adverse event* that result in any of the following outcomes:

- Death
- Is life-threatening experiences (places the subject at immediate risk of death from the event as it occurred)
- Unplanned hospitalization equal or greater than 24 hours)) or prolongation of existing hospitalization
- A persistent or significant disability/incapacity
- A congenital anomaly/birth defect
- Any other adverse event that, based upon appropriate medical judgment, may jeopardize the subject’s health and may require medical or surgical intervention to prevent one of the outcomes listed above (examples of such events include allergic bronchospasm requiring intensive treatment in the emergency room or at home, blood dyscrasias of convulsions that do not result in inpatient hospitalization, or the development of drug dependency or drug abuse).

Unanticipated problem (UP) - Any incident, experience or outcome that **meets all three** of the following criteria:

1. Unexpected (in term nature, severity, or frequency) given the following: a) the research procedures described in the protocol-related documents such as the IRB approved research protocol, informed consent document or Investigator Brochure (IB); and b) the characteristics of the subject population being studied; **AND**

2. Related or possibly related to participation in the research (possibly related means there is a reasonable possibility that the incident, experience, or outcomes may have been caused by the drugs, devices or procedures involved in the research); **AND**
3. Suggests that the research places subjects or others at greater risk of harm (including physical, psychological, economic, or social harm) than previously known or recognized.

Protocol Violation- A protocol violation is an accidental or unintentional change to or noncompliance with the IRB-approved protocol that increases risk or decreases benefit and/or affects the subject's rights, safety, welfare, and/or the integrity of the data. Examples of incidents that may be considered violations include: enrolling a participant who does not meet the inclusion criteria; obtaining verbal consent before the initiation of study procedures when the IRB requires signed, written informed consent; and failure to collect screening labs before initiation of study procedures.

Protocol Deviation- A deviation is an unintentional change to or noncompliance with the research protocol that does not have a significant effect on the subject's rights, safety or welfare, and/or on the integrity of the data. Deviations may result from the action of the participant, researcher, or research staff. Examples of deviations include: a rescheduled visit; an incomplete study visit; and failure to collect ancillary study measures (e.g., questionnaire, baseline BP).

Reporting Requirements to the CFCCC DSMB

ADVERSE EVENT/ SERIOUS ADVERSE EVENTS

Event Type	Reporting Timeframe

 • Unexpected SAE, all attributions (unrelated, unlikely, possibly, probably, definite) • Grades 3-5 	5 days from date the PI is aware of the event

 • Expected AE/SAE, all attributions (unrelated, unlikely, possibly, probably, definite) • Grades 1-5 	Progress review as aggregate report

DEVIATIONS/VIOLATIONS

Event Type	Reporting Timeframe
An incident that significantly affects subject safety or data integrity (e.g. wrong dosage of drug administered, safety procedures not being conducted at specific time points).	5 days from the date the PI is aware of the event
All incidents that occurred during the study	At the time of progress review as aggregate reports

UNANTICIPATED PROBLEMS

Unanticipated problems that are adverse events must be reported within 24 hours of reporting to the IRB for review.

Treatment with the NOVOTTF-200A is not expected to cause any serious side effects. However, it is possible that investigational treatment will cause any of the following:

- Local warmth and tingling sensation beneath the electrodes
- Allergic reaction to the plaster or to the gel
- Skin breakdown
- Infection at the sites of electrode contact with the skin
- Electrode overheating leading to pain and/or local skin burns
- Headache
- Fatigue
- Seizures

Adverse events and complications associated with the underlying AA disease process, which are unlikely but unknown if related to treatment with NOVOTTF-200A might include the following adverse events:

- Seizure, including Status Epilepticus
- Neurological and functional decline
- Headaches, nausea and/or vomiting
- Death

As defined by the ICH Guidelines for Good Clinical Practice E2A (CPMP/ICH/377/95), an adverse event (AE) is any untoward medical occurrence in a patient administered a medicinal product and which does not necessarily have to have a causal relationship with this treatment. An adverse event can therefore be any unfavorable and unintended sign (for example, an abnormal laboratory finding), symptom, or disease temporally associated with the use of a medicinal product, whether or not considered related to this medicinal product. Adverse events include the following:

- All suspected medication adverse reactions
- All reactions from medication overdose, abuse, withdrawal, sensitivity, or toxicity.
- Apparently unrelated illnesses, including the worsening of a preexisting illness
- Injury or accidents. Note that if a medical condition is known to have caused the injury or accident (a fall secondary to dizziness), the medical condition (dizziness) and the accident (fall) should be reported as 2 separate adverse events.
- Abnormalities in physiological testing or physical examination findings that require clinical intervention or further investigation (beyond ordering a repeat [confirmatory] test).
- Laboratory abnormalities that require clinical intervention or further investigation (beyond ordering a repeat [confirmatory] test) unless they are associated with an already reported clinical event. Laboratory abnormalities associated with a clinical event (elevated liver enzymes in a patient with jaundice) should be captured in the source documents.

Each adverse event is to be classified by the investigator as serious or non-serious. This classification of the gravity of the event determines the reporting procedures to be followed.

Grading of an Adverse Event:

The descriptions and grading scales found in the revised NCI Common Toxicity Criteria (CTC) version 4.03 will be utilized for assessing severity of adverse events. If the toxicity is not characterized adequately by the NCI toxicity scale, the investigator will use the adjectives MILD, MODERATE, SEVERE to describe the maximum intensity of the adverse event. For purposes of consistency, these intensity grades are defined as follows:

- MILD Grade 1 Transient or minimal symptoms, no change in activity or need for medication
- MODERATE Grade 2 Symptomatic change, interferes to some extent with patient's usual function
- SEVERE Grade 3 Incapacitating, significantly interferes with patient's usual function

Determination of Causality of Adverse Events

The relationship of the adverse event to the study treatment must be specified using the following definitions:

None:

The event is clearly related to an event that may be due to environmental or accidental occurrence or other factors such as the subject's clinical state, therapeutic interventions, or concomitant drugs administered to the subject.

Unlikely

The event is most likely produced by other factors such as the subject's clinical condition, therapeutic interventions, or concomitant drugs administered to the subject **and** does not follow a known response pattern to the study device.

Possible

The event follows a reasonable temporal sequence from the time of drug administration or use of device, **and/or** follows a known response pattern to the study drug or device, **but** could have been produced by other factors such as the subject's clinical condition, therapeutic interventions, or concomitant drugs administered to the subject.

Probable

The event follows a reasonable temporal sequence from the time of drug administration or use of device, **and** follows a known response pattern to the study drug or device, **and** cannot be reasonably explained by other factors such as the subject's clinical condition, therapeutic interventions, or concomitant drugs administered to the subject.

Definite

The event follows a reasonable temporal sequence from the time of drug administration or use of device, **and** follows a known response pattern to the study drug or device, **and** cannot be reasonably explained by other factors such as the subject's clinical condition, therapeutic interventions, or concomitant drugs administered to the subject, **and either** occurs immediately following study drug administration or use of device **or** improves on stopping the study drug or device, **or** reappears on repeat exposure

Serious Adverse Events

An adverse event that meets one or more of the following criteria/outcomes is classified as serious:

- Death
- Life-threatening (i.e., at immediate risk of death)
- Inpatient hospitalization or prolongation of existing hospitalization
- Persistent or significant disability/incapacity
- Congenital anomaly/birth defect

Important adverse events that may not result in death, may not be life-threatening, or do not require hospitalization may be considered serious when, based upon appropriate medical judgment, they may acutely jeopardize the patient without immediate medical intervention to prevent one of the outcomes listed above. Serious may also include any other event that the investigator or company judges to be serious. In addition, the site is responsible for reporting serious adverse events to their local IRB according to their institutional requirements. Death due to disease progression need not be reported to the study monitor. These SAEs will be captured in the CRFs as described for regular AEs.

Routine Adverse Event Reporting

All adverse events must be reported in the source documentation and CRFs with appropriate information, including severity and rating of causality to the study drug/treatment. Adequate source documentation must be available to characterize the severity, duration and causality of each reported adverse event.

Unanticipated Adverse Device Effect Event (UADE) Reporting

Any potential unanticipated adverse device effect (UADE) will be reported to the local IRB within 10 days of the investigator learning of the event. The investigator will investigate whether the adverse event is a UADE and, if so, report the UADE to the manufacturer, as soon as possible but no later than 3 days after first learning of the event. Expedited report for FDA submission to follow within 10 working days after the investigator first learning of the event.

The report will contain the following:

- The initials of the subject, subject ID #, protocol # and title

- The date the event occurred
- A description of the UADE
- An explanation of how the UADE was handled
- A description of the subject's condition
- Indication if the subject remains on the study
- Indication if the event is considered related to the NovoTTF-200A
- Indication if an amendment to the protocol and/or consent form is recommended as a result

Eliciting Adverse Event Information

The investigator is to report all directly observed adverse events and all adverse events spontaneously reported by the trial patient using concise medical terminology. In addition, each subject will be questioned about adverse events at each clinic visit following initiation of treatment. The question asked will be, “Since your last clinic visit have you had any health problems?”

Adverse Event Reporting Period

The adverse event reporting period will begin immediately following initiation of treatment with the NOVOTTF-200A device. Adverse events will be collected for two months following treatment termination. All adverse events that occur in trial patients during the adverse event reporting period specified in the protocol must be reported on the CRFs, whether or not the event is considered study treatment-related. In addition, any known untoward event that occurs beyond the adverse event reporting period that the investigator assesses as possibly related to the investigational medication/product should also be reported as an adverse event.

Follow-up of Unresolved Adverse Events

All adverse events should be followed until they are resolved or the investigator assesses them as chronic or stable or the patient’s participation in the trial ends. In addition, all serious adverse events and those non-serious events assessed by the investigator as probably related to the investigational medication/product should continue to be followed even after the patient’s participation in the trial is over. Such events should be followed until they resolve or until the investigator assesses them as “chronic” or “stable.” Resolution of such events is to be documented on the appropriate CRF.

An adverse event (AE) is any noxious, unintended, or untoward medical occurrence that may appear or worsen in a subject during the course of a study. It may be a new intercurrent illness, a worsening concomitant illness, an injury, or any concomitant impairment of the subject’s health, including laboratory test values, regardless of etiology. Any worsening (i.e., any clinically significant adverse change in the frequency or intensity of a pre-existing condition) should be considered an AE. A diagnosis or syndrome should be recorded on the AE page of the CRF rather than the individual signs or symptoms of the diagnosis or syndrome.

All subjects will be monitored for AEs during the study. Assessments may include monitoring of any or all of the following parameters: the subject’s clinical symptoms, laboratory,

pathological, radiological or surgical findings, physical examination findings, or findings from other tests and/or procedures.

All SAEs will be recorded by the Investigator from the time the subject signs informed consent until 28 days after the last NovoTTF-200A treatment and those SAEs made known to the investigator at any time thereafter that are suspected of being related to study treatment. AEs are recorded from the start of the initial treatment. AEs occurring before the treatment are considered medical history and should be recorded on the medical history CRF. AEs and serious adverse events (SAEs) will be recorded on the AE page of the CRF and in the subject's source documents. All SAEs must be reported to NovoCure within 24 hours of the Investigator's knowledge of the event by facsimile, or other appropriate method, using the SAE Report Form, or approved equivalent form.

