10.2.5. Duration

For both AEs and SAEs, the Investigator will provide a record of the start and stop dates of the event. For AEs that become SAEs, the start date of the SAE will be when the seriousness criteria are met. The original AE will have a stop date the same as the start date of the SAE. The SAE will have a stop date of when the seriousness criteria are no longer met. If the AE continues after the seriousness criteria are no longer met, then a new AE will be recorded with a start date the same as the SAE stop date and a stop date when the AE is completely resolved. In all cases, the AE must have the same verbatim term throughout. Within the duration of the SAE or AE, the maximum grade should be used to categorize severity.

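### The fallback severity scale in Section 10.1 stops at Grade 3, so incapacitating, life-threatening and fatal events graded on it would share one row of the severity tables

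*Combined protocol and SAP*

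**What the plan says.** Section 10.1, under the grading of adverse events, makes the NCI scale the main instrument: the "grading scales found in the revised NCI Common Toxicity Criteria (CTC) version 4.03 will be utilized for assessing severity of adverse events". It then gives a second instrument for events that the first does not describe well: "If the toxicity is not characterized adequately by the NCI toxicity scale, the investigator will use the adjectives MILD, MODERATE, SEVERE". The purpose of those words is "to describe the maximum intensity of the adverse event". Each carries a grade number: mild is 1, moderate is 2, and the last entry reads "SEVERE Grade 3 Incapacitating, significantly interferes with" the patient's usual function. No level follows it.

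Three other places bear on the point:

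- **DSMB table, Section 10.1.** Unexpected serious events of Grades 3 to 5 are reported within five days. Expected events of Grades 1 to 5 go into aggregate progress reports.
- **Section 9.2.** "Safety and tolerability of NOVOTTF-200A treatment will be based on the incidence and severity of adverse events and toxicities", presented in individual listings and summary tables.
- **Section 10.2.5.** Within an event's duration, "the maximum grade should be used to categorize severity".

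Seriousness is a separate classification. The criteria in Section 10.1 include death and "Life-threatening (i.e., at immediate risk of death"), and Section 10.2.2 repeats both. Section 10.2.3 says that severity and seriousness are different things and that regulatory duties follow seriousness.

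**The concern.** The fallback attaches grade numbers to its adjectives, so its results enter the tables on the same numeric axis as NCI grades. That axis runs to 5 elsewhere in the protocol, but on the fallback it runs only to 3. The investigator is told to record the maximum intensity of the event on a scale whose maximum is incapacity. Anything worse has no value of its own.

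At stake is how accurately the severity summary reads. Safety is a secondary objective, and Section 9.2 rests it on incidence and severity. A table by maximum grade in which the Grade 3 row may hold a life-threatening or fatal event, with nothing to show it, does not do what a reader expects. The fallback exists for events that the standard scale does not fit, and those are events for which the reader has least to go on besides the grade.

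**Working it through.** The plan states no figure on this point and no formula applies. The check sets the grading text against every other use of grades.

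**1. Levels available.** The DSMB table implies five grades, 1 to 5. The fallback defines three, 1 to 3. The shortfall is 5 − 3 = 2 levels, Grades 4 and 5.

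**2. Whether another section supplies them.** Section 10.2.3 requires a severity assessment for every adverse event and serious adverse event but defines no levels. Section 10.2.5 says to take the maximum grade but adds none. Section 9.2 names version 4.03 of the toxicity criteria and does not extend the fallback. Nothing else fills the gap.

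**3. What the rule gives when applied to an event the NCI scale does not adequately describe.**

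| Worst state reached | Fallback grade | Place in the protocol's 1–5 range |
|---|---|---|
| Minimal symptoms | 1 | 1 |
| Some interference with function | 2 | 2 |
| Incapacitating | 3 | 3 |
| Life-threatening | 3 (highest available) | none defined on the fallback |
| Fatal | 3 (highest available) | none defined on the fallback |

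The last three rows collapse into one value. Taking the maximum grade under Section 10.2.5 does not separate them, because the maximum is 3 in each case.

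**4. Where the grade is used.**

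- *Severity tables (Section 9.2):* affected, since they depend on the grade.
- *Serious-event reporting (Sections 10.2.2 and 10.5.1):* not affected. Death and threat to life qualify at any grade, and the 24-hour report follows from seriousness.
- *Unanticipated device effects (Section 10.1):* not affected. The report is descriptive and has no grade threshold.
- *DSMB five-day row:* not affected. An unexpected serious event capped at Grade 3 is still within Grades 3 to 5.
- *Other stated grade thresholds:* inclusion criterion 7 uses Grade 1 or lower, and footnote 15 to the schedule of assessments uses Grade 2 or higher. Neither separates Grade 3 from Grades 4 and 5.
- *Stopping for intolerability (Section 8.1):* clinical judgment, with no grade count.

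Of these uses, only the severity tables change.

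**The case against.** The strongest reply is that the protocol puts threat to life on a different axis on purpose. Section 10.2.3 treats severity as intensity and leaves danger to life to the seriousness criteria. Section 10.1 calls the fallback levels intensity grades. A three-level intensity scale beside a serious/non-serious classification is a coherent arrangement. A life-threatening or fatal event would also carry a serious-event form with a detailed description, be followed to an outcome that can include death if unresolved when participation ends, and appear in the individual listings of a trial of up to 36 subjects. It would be hard to overlook.

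Most of this stands, and it is why the point is minor. It does not remove the mismatch. The fallback levels are numbered as grades and so join a scale that runs to 5 elsewhere. The serious flag cannot restore the distinction inside a severity table, because it also covers hospitalisation and disability.

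Three stronger readings are tempting, and the documents support none of them.

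- **Deaths or life-threatening events would go unreported or be reported late.** Reporting follows seriousness, and the DSMB five-day row already takes in Grade 3.
- **A Grade 4–5 rate for the device would be biased low.** No such rate, bound or threshold is planned. Any figure for the shift would describe an assumed event and a statistic that is not in the plan.
- **Electrical or other device failures are the events that would need the fallback.** What is graded is the patient's clinical event, and the device harms listed in Section 10.1, such as burns, skin breakdown, infection and seizures, are ordinary clinical terms. The documents do not show which events the NCI scale would fail to describe. Whether version 4.03 has a general entry for unlisted events cannot be checked from them.

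**Conclusion.** The point holds as a mismatch in severity tabulation. The text is mandatory, the fallback ends two grades short of the range used elsewhere in the protocol, and no other section completes it. It is therefore a rule that gives a wrong grade in the cases it reaches, and not merely an omitted detail.

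The consequence is minor. The primary endpoint, the futility look, the reporting timelines and every named safety statistic are unchanged. No numerical size is given because the documents offer no basis for how often the fallback would be used.

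The conclusion assumes that fallback grades are tabulated together with NCI grades, which their shared numbering implies but Section 9.2 does not state. It also assumes that an investigator could judge the NCI scale inadequate for an event that threatens life or kills. If that never happens, the tables are unaffected.

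**What to change.** Add two levels to the fallback list in Section 10.1, life-threatening as Grade 4 and fatal as Grade 5, and carry them into any CRF completion guidance, so that the fallback matches the five grades in the DSMB table.

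The cost is two lines of text. It changes event classification only and leaves treatment, eligibility, sample size and stopping as they are. It is best made before grades are assigned: regrading afterwards, in an open-label single-centre trial, would be a retrospective judgment by people who know the outcome. If grades have already been assigned on the fallback, the safety report can footnote any fallback Grade 3 event that met the death or life-threatening criterion.
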